#### 20.6.2 Analysis

Population: FAS

Stratification: Table: NA

Statistics: Number of patient (n) and percentage (%) will be summarised for the patient eyes with at least one duration of interval between injections ≥ 12 weeks.

## 20.7 Percentage of patients with absence of intra-retinal fluid (IRF) from baseline to week 16 and week 56

#### 20.7.1 Variables and Derivations

Variables:

• Intra-retinal fluid results from optical coherence tomography eCRF form

#### Derivations:

Time Frame: Baseline to week 16 and Baseline to week 56

For baseline visit, if "Intra-retinal fluid Results" is reported as "Absent" then

- At week 16 and week 56, If "Intra-retinal fluid Results (Post Baseline)" is reported as "Same as baseline" then corresponding results will be considered as "Absence" of intra-retinal fluid.
- At week 16 and week 56, If "Intra-retinal fluid Results (Post Baseline)" is reported as ("Increased" or "Present") then corresponding results will be considered as "Increased" of intra-retinal fluid.

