#### 6.2 Secondary Objectives

- 1. To evaluate the effectiveness of brolucizumab in the management of nAMD in terms of change in best-corrected visual acuity (BCVA) from baseline to Week 56.
- 2. Characterize the number of anti-VEGF injections, number of non-injection visits, and total number of visits during the 56 weeks of treatment with brolucizumab.
- 3. Estimate the percentage (%) of patient eyes with anti-VEGF injection intervals q8w and q12w during the 56 weeks of treatment with brolucizumab.
- 4. Estimate effect of brolucizumab on fluid from baseline to week 16 and week 56.
- 5. Estimate effect of brolucizumab on central subfield thickness (CST) from baseline to week 16 and week 56.

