#### 7.2.1 Inclusion criteria

- 1. Female or male, treatment naïve patient with ≥50 years of age, with neovascular agerelated macular degeneration (nAMD).
- 2. Patient or legally acceptable representative (LAR) willing to voluntarily provide signed informed consent for participation in the study.

Note: In case where both eyes are affected, data of only one eye ['study eye'] will be recorded. Selection of the eye to be considered for the purpose of the study [referred to as 'study eye'] will be as per the Investigator's discretion.

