#### Secondary Endpoints Analysis

The secondary endpoints will evaluate the effectiveness of brolucizumab in terms of change in the following parameters from Baseline to the end of week 56. BCVA at baseline, week 16 and 56 including the change will be summarized with standard descriptive statistics.

- Mean change in BCVA from baseline to week 16 and week 56 as measured by ETDRS letters.
- Percentage (%) of patient eyes with gain in BCVA of 15/10/5 ETDRS letters or more at week 16 and week 56
- Percentage (%) of patient eyes with loss in BCVA of 15/10/5 ETDRS letters or more at week 16 and week 56.
- Number of anti-VEGF injections, non-injection visits and total number of visits
- Percentage (%) of patient eyes with at least one duration of interval between injections ≥ 8 weeks but <12 weeks.

- Percentage (%) of patient eyes with at least one duration of interval between injections ≥ 12 weeks.

- Percentage of patients with absence of intra-retinal fluid from baseline to week 16 and week 56.
- Percentage of patients with absence of sub-retinal fluid from baseline to week 16 and week 56.
- Estimated change in CST (in µm) from baseline to week 16 and week 56.

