#### And

For baseline visit, if "Intra-retinal fluid Results" is reported as "Present" then

- At week 16 and week 56, If "Intra-retinal fluid Results (Post Baseline)" is reported as "Completely resolved" then corresponding results will be considered as "Absence" of intra-retinal fluid.
- At week 16 and week 56, If "Intra-retinal fluid Results (Post Baseline)" is reported as "Decreased" then corresponding results will be considered as "Decreased" of intra-retinal fluid.

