#### 20.7.2 Analysis

Population:	FAS
Stratification:	Table: NA
Statistics:	Number of patient (n) and percentage (%) will be presented
	for patients with absence of IRF from baseline to week 16 and
	week 56.

Additionally, number of patient (n) and percentage (%) for patients with increased and decreased IRF from baseline to week 16 and week 56 will be presented.

### 20.8 Percentage of patients with absence of sub-retinal fluid (SRF) from baseline to week 16 and week 56

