#### Derivations:

Time Frame: Baseline to week 16 and Baseline to week 56

For baseline visit, if "Sub-retinal fluid Results" is reported as "Absent" then

- At week 16 and week 56, If "Sub-retinal fluid Results (Post Baseline)" is reported as "Same as baseline" then corresponding results will be considered as "Absence" of Sub-retinal fluid.
- At week 16 and week 56, If "Sub-retinal fluid Results (Post Baseline)" is reported as ("Increased" or "Present") then corresponding results will be considered as "Increased" of Sub-retinal fluid.

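### The fluid Absence percentage combines eyes that were already dry at baseline with eyes whose fluid resolved, so the planned rows do not show the resolution rate and answer Objective 4 only in part

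*SAP*

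**What the plan says.** Objective 4 (protocol 6.2) reads "Estimate effect of brolucizumab on fluid from baseline to week 16 and week 56". Protocol 7.6.5 turns it into two percentages, one for each fluid; the first is "Percentage of patients with absence of intra-retinal fluid from baseline to week 16 and week 56".

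The SAP derivations send two kinds of eye to the same category:

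- Fluid Absent at baseline (SAP 20.7.1): a later result that "is reported as 'Same as baseline' then corresponding results will be considered as 'Absence' of intra-retinal fluid".
- Fluid Present at baseline (same section): a later result that "is reported as 'Completely resolved' then corresponding results will be considered as 'Absence' of intra-retinal fluid".

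SAP 20.8.1 repeats the scheme for the other fluid: a result that "is reported as 'Same as baseline' then corresponding results will be considered as 'Absence' of Sub-retinal fluid".

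The analysis population is the Full Analysis Set, which is every consented patient given one or more brolucizumab injections (SAP 6.2). The tables are not stratified (SAP 20.7.2, 20.8.2). Rows for increased and decreased fluid are added. These sections call for n and % only, whereas the BCVA gain and loss tables (SAP 20.2.2, 20.3.2) also have Clopper-Pearson intervals.

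Eligibility (protocol 7.2.1, 7.2.2) asks for treatment-naïve nAMD at age 50 or over, and protocol 7.2 adds that brolucizumab must already have been chosen. None of the criteria mentions intra-retinal or sub-retinal fluid. The baseline summaries name BCVA but neither fluid (protocol 7.6.3, SAP 11.1).

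**The concern.** An eye with no fluid of a given type at baseline has none to resolve. If it stays that way, it adds to the Absence count exactly as an eye that dried out under treatment does. The two fluids are scored separately, so an eye with only sub-retinal fluid starts as a candidate for intra-retinal Absence, and the reverse. Some eyes can therefore start dry for one fluid even if every enrolled eye had fluid of some kind.

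Objective 4 asks about change from baseline. A percentage that moves with the baseline mix does not show that change by itself, and the visible plan has no baseline fluid summary or baseline-by-visit table to read it against. The protocol also plans a descriptive comparison with HAWK and HARRIER (protocol section 5), where a difference in baseline mix could be taken for a difference in response.

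**Working it through.** The plan states no figure for these endpoints, so there is none to reproduce.

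**Identity.** Let q be the share of eyes without that fluid at baseline, s the share of those still without it at the visit, and r the share of eyes with fluid at baseline that resolve completely. Then

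reported Absence = q·s + (1 − q)·r, and its excess over r is q·(s − r).

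The documents give none of q, s or r. All values below are assumptions.

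**Step 1: no change in any eye** (s = 1, r = 0). Absence = q. Over an assumed range of q from 10% to 60%, the table would read 10% to 60%.

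**Step 2: a fixed resolution rate.** With r = 40% and s = 95%:

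- q = 30%: 0.285 + 0.280 = 56.5%
- q = 50%: 0.475 + 0.200 = 67.5%
- q = 60%: 0.570 + 0.160 = 73.0%

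**Step 3: a case with little distortion.** With q = 10%, s = 95% and r = 70%: 0.095 + 0.630 = 72.5%, which is 2.5 points above r.

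**Step 4: reading backwards.** Suppose 70% is reported and s = 1. Then r = (0.70 − q)/(1 − q), which is 66.7% at q = 10%, 50% at q = 40%, 25% at q = 60% and 0% at q = 70%.

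**Step 5: do the added rows settle it?** By the written rules, Increased arises only from eyes Absent at baseline and Decreased only from eyes Present at baseline. Eyes Present at baseline and later *Same as baseline* or *Increased* have no category. Take N = 105, the number enrolled (SAP 8.1), with assumed counts: Absence 74, Increased 5, Decreased 16, no category 10. Let a be the number of Absence eyes that started dry. Then:

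- eyes dry at baseline = a + 5
- eyes resolved = 74 − a
- eyes with fluid at baseline = (74 − a) + 16 + 10 = 100 − a
- r = (74 − a)/(100 − a)

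Nothing in the planned rows fixes a. The same table fits each line below:

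| Dry at baseline | a | Resolved / with fluid at baseline | r | Clopper-Pearson 95% CI |
|---|---|---|---|---|
| 10 | 5 | 69/95 | 72.6% | 62.5 to 81.3 |
| 21 | 16 | 58/84 | 69.0% | 58.0 to 78.7 |
| 42 | 37 | 37/63 | 58.7% | 45.6 to 71.0 |
| 63 | 58 | 16/42 | 38.1% | 23.6 to 54.4 |

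In all four the reported Absence is 74/105 = 70.5%. The first line implies new fluid in 5 of 10 dry eyes, so it is an extreme case, but the table alone does not exclude it.

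**The case against.** The strongest reply is that the SAP does what the protocol asks. The endpoint is the percentage of patients with absence of fluid, and an eye with none at Week 16 is correctly counted as absent. Complete resolution among eyes that had fluid is a different quantity. This stands: the derivation is not an error, and the pooled percentage should stay.

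It is also fair that the Decreased and Increased rows carry some information on change, and that protocol 7.6.1 has CRF data listed, so resolution could be counted by hand. Both points limit the concern, but Step 5 shows that the summary rows still do not give the rate.

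The size is open. Treatment-naïve eyes already chosen for brolucizumab may seldom lack fluid, though the criteria do not guarantee it and the separate scoring of the two fluids still applies. Step 3 shows that the gap can be a few points.

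A reader might also infer that the figure cannot be set against the phase 3 trials. The documents do not give those trials' fluid definitions, so whether a pooled or a restricted percentage would match them cannot be judged here.

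**Conclusion.** The point holds in a limited form. The Absence percentage validly describes eyes free of that fluid at a visit, but it depends on the baseline mix. The visible text plans no summary of baseline fluid, and the resolution rate is not identifiable from the planned rows. Objective 4 is therefore partly answered. Some SAP pages were not available, so the lack of a baseline fluid table is stated only for the text that could be read.

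A reader might go further and conclude that the endpoint cannot answer Objective 4 at all, or that it overstates the drug's effect. The documents do not support either. The endpoint is the protocol's own, the added rows show some change, and a single-arm study yields within-eye change, not a controlled drug effect, under any definition.

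The classification follows directly from the text. The size rests wholly on assumed q, s and r. It runs from 2.5 points (q = 10%, r = 70%, s = 95%) to the limiting case in which the whole reported figure is the baseline dry share.

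**What to change.** Keep the overall Absence percentage in SAP 20.7 and 20.8 as the protocol endpoint, and print the baseline percentage without that fluid beside it. Add two rows for each fluid at Weeks 16 and 56:

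- (a) complete resolution among study eyes with that fluid Present at baseline;
- (b) new fluid among study eyes with it Absent at baseline.

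Give each as n/N with a Clopper-Pearson 95% interval. State that (a) is used when interpreting Objective 4, as within-eye change and not as a controlled drug effect.

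No new data are needed, because baseline and post-baseline results are already on the OCT form. No endpoint is redefined, which matters because enrolment is complete (SAP 8.1); describe the rows as additions. The cost is a few table rows, and a smaller denominator and wider interval for (a). In the illustration, 74/105 has an interval of 60.8 to 79.0 (18.2 points wide), against 23.6 to 54.4 (30.8 points) for 16/42. The figure for (a) will also probably look less favourable than the overall percentage.

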#### And

For baseline visit, if "Intra-retinal fluid Results" is reported as "Present" then

- At week 16 and week 56, If "Intra-retinal fluid Results (Post Baseline)" is reported as "Completely resolved" then corresponding results will be considered as "Absence" of intra-retinal fluid.
- At week 16 and week 56, If "Intra-retinal fluid Results (Post Baseline)" is reported as "Decreased" then corresponding results will be considered as "Decreased" of intra-retinal fluid.

#### 20.7.2 Analysis

Population:	FAS
Stratification:	Table: NA
Statistics:	Number of patient (n) and percentage (%) will be presented
	for patients with absence of IRF from baseline to week 16 and
	week 56.

Additionally, number of patient (n) and percentage (%) for patients with increased and decreased IRF from baseline to week 16 and week 56 will be presented.

### 20.8 Percentage of patients with absence of sub-retinal fluid (SRF) from baseline to week 16 and week 56

#### 20.8.1 Variables and Derivations

Variables:

• Sub-retinal fluid results from optical coherence tomography eCRF form

#### Derivations:

Time Frame: Baseline to week 16 and Baseline to week 56

For baseline visit, if "Sub-retinal fluid Results" is reported as "Absent" then

- At week 16 and week 56, If "Sub-retinal fluid Results (Post Baseline)" is reported as "Same as baseline" then corresponding results will be considered as "Absence" of Sub-retinal fluid.
- At week 16 and week 56, If "Sub-retinal fluid Results (Post Baseline)" is reported as ("Increased" or "Present") then corresponding results will be considered as "Increased" of Sub-retinal fluid.

#### And

For baseline visit, if "Sub-retinal fluid Results" is reported as "Present" then

- At week 16 and week 56, If "Sub-retinal fluid Results (Post Baseline)" is reported as "Completely resolved" then corresponding results will be considered as "Absence" of Sub-retinal fluid.
- At week 16 and week 56, If "Sub-retinal fluid Results (Post Baseline)" is reported as "Decreased" then corresponding results will be considered as "Decreased" of Sub-retinal fluid.

#### 20.8.2 Analysis

Population:	FAS
Stratification:	Table: NA
Statistics:	Number of patient (n) and percentage (%) will be presented
	for patients with absence of SRF from baseline to week 16
	and week 56.
	Additionally, number of patient (n) and percentage (%) for
	patients with increased and decreased SRF from baseline to
	week 16 and week 56 will be presented.

# 20.9 Estimated change in CST (in μm) from baseline to week 16 and week 56 20.9.1 Variables and Derivations

Variables:

• Central Subfield Retinal Thickness Results (in µm)

Derivations:

• Time Frame: Baseline to week 16 and Baseline to week 56.

Note: Data of study eye type (i.e., right, or left) will be used in post baselines visit then respective baseline study eye type data will be considered for the analysis.

#### 20.9.2 Analysis

Population:For Table: FAS
For Listing: SCRStratification:Table: NA
Listings: By patient and date of testStatistics:The summary statistics for absolute and absolute change
from baselines will be presented in the table as number of
observations (n), arithmetic mean, standard deviation (SD),
lower quartile, median, upper quartile, minimum and
maximum. Point estimate, Two-sided 95% confidence
intervals and p-values for within-patient changes across time
will be presented using paired t-test. The listing will be
presented.

#### 21. Other assessments

The following assessments will be presented in data listings as per eCRF for the SCR population:

- Fundus Photography
- Fluorescein Angiography

#### 22. Revision history

Version	Date	Change
1.0	10-May-2023	Initial Version

# 23. Appendix 1: Programming Conventions for Tables, Data Listings and Figures (TLFs)

#### 23.1 Paper Size, Orientation and Margins

The margin, page size and line size specifications as stipulated in Table 23.1 will be used for the presentation of all TLFs.

	Landscape	Portrait
Margins (Inches):		
Тор	1.25	1
Bottom	1	1
Left	1	1.25
Right	1	1
Header (Inches)	0.5	0.5
Footer (Inches)	0.5	0.5
SAS ® specifications:		
PAGESIZE	46	67
LINE SIZE	134	93

#### Table 23.1: Output margin, page size and line size specifications

The font type "Courier New" should be used as default for tables and data listings, with a font size of 8. The font color should be black. No bolding, underlining and italics are permitted.

Figures should have a default font of "Times Roman", "Helvetica" or "Courier New".

#### 23.3 Header Information

Headers should be defined as follows:

- The header should be placed at the top of the page (same place on each page).
- The sponsor name should appear in row 1, left-aligned.
- The word "CONFIDENTIAL" should appear in row 1, right-aligned.
- The protocol number should appear in row 2, left-aligned.
- The page identification in the format Page X of Y (where Y is the total number of pages for the TLF) should appear in row 2, right-aligned.
- The TLF identification number should appear in row 3, centered.
- The TLF title should start in row 4, centered.

- The TLF population should appear in row 5, centered. The population should be spelled out in full, e.g. Safety analysis population in preference to Safety analysis population.
- Row 6 should be a continuous row of underscores ('\_') (the number of underscores should equal the line size).
- Row 7 should be a blank line.
- Mixed case should be used for titles.
- Titles should not contain quotation marks or footnote references.
- The column headings should be underlined with a row of underscores ('\_').
- Column headings spanning more than one column should be underlined and have underscores on either side of the title and should be centered.
- Column headings containing numbers should be centered.
- Column headings should be in mixed case.
- In general, the analysis population count should appear in the column header in the form "(N=XX)".

#### 23.4 Table and Data Listing Table, Listing and Figure (TLF) Conventions

#### 23.4.1 General

- The first row in the body of the table or data listing should be blank.
- The left-hand column should start in Column 1. No indenting or centering of the TLF should occur.
- Rounding should be done with the SAS® function ROUND.
- Numerical values in tables should be rounded, not truncated.
- Numerical values should be decimal point aligned.
- Text values should be left aligned.
- The first letter of a text entry should be capitalized.
- The study drug should appear first in tables with treatment group as columns.
- All variables contained on the eCRF (which have data present) should appear in the data listings, along with all derived data appearing in the corresponding tables.
- The width of the TLF should match the line size.

#### 23.4.2 Univariate statistics

• Statistics should be presented in the same order across tables (i.e., n, mean, SD, minimum, median and maximum).

- If the original data has N decimal places, then the summary statistics should have the following decimal places:
  - Minimum, maximum and CV (%): N
  - Mean and median: N + 1.
  - SD: N + 2.

#### 23.4.3 Frequencies and percentages [n, (m) and %]

- Mentions should be reported inside parentheses, with one space between the count and the left parenthesis of the mentions. An example is given below:
  - o **124 (645)**
- Percent values should be reported inside parentheses, with one space between the right parenthesis of the mention and the left parenthesis of the percentage. Parentheses should be justified to accept a maximum of 100.0 as a value and padded with blank space if the percent is less than 100.0. An example is given below:
  - o **77 (156) (100.0)**
  - o 50 (56) ( 64.9)
  - o **0 (0) ( 0.0)**
- Percentages will be reported to one decimal place, except percentages <100.0 but >99.9 will be presented as '>99.9' (e.g., 99.99 is presented as >99.9); and percentages <0.1 will be presented as '<0.1' (e.g., 0.08 is presented as <0.1). Rounding will be applied after the <0.1 and >99.9 rule.
  - o **(<0.1)**
  - o (6.8)
  - o **(>99.9)**
- Percentages may be reported to 0 decimal places as appropriate (for example, where the denominator is relatively small).
- Where counts are zero, mentions of 0 and percentages of 0.0 should appear in the table.

#### 23.4.4 Confidence intervals (CIs)

• CIs should be presented with one additional decimal place as that of the raw data, and SDs and standard errors (SEs) with two additional decimal places as that of the raw data.

• Cls should be justified so that parentheses displayed on consecutive lines of a table "line up".

#### 23.4.5 P-values

 P-values should be reported to four decimal places. If p-value is 0.0000 then we present it <0.0001 and p-value is 1.0000 then it >0.9999.

#### 23.4.6 Ratios

• Ratios should be reported with one additional decimal place as that of the raw data.

#### 23.4.7 Spacing

• There should be a minimum of 1 blank space between columns (preferably 2).

#### 23.4.8 Missing values

- A "0" should be used to indicate a zero frequency.
- A blank will be used to indicate missing data in data listings.

#### 23.5 Figure output conventions

Figures should be provided in RTF files using the SAS® Output Delivery System (ODS).

#### 23.6 Dates and times

Depending on data available, dates and times will take the form ddMMMyyyy and hh:mm.

#### 23.7 Spelling format

The spelling format to be used is English US.

#### 23.8 **Presentation of treatment groups**

Treatment:

• Brolucizumab

#### 23.9 Presentation of visits

- Visit 1 (Week 0)
- Visit 2 (Week 4
- Visit 3 (Week 8)
- Visit 4 (Week 16)
- Visit 5 (Week 20)
- Visit 6 (Week 24)
- Visit 7 (Week 32)

- Visit 8 (Week 40)
- Visit 9 (Week 44)
- Visit 10 (Week 48)
- Visit 11 (Week 56)

## 24. Appendix 2: Partial date conventions and Concomitant medication guidelines

The whole missing date will not be imputed for this study; only partial date imputation will be performed. Conventions pertaining to partial dates are presented.

#### (CM) Concomitant Imputation Missing Medication Start Date Dav If CM start Month = Treatment start month and CM start Year = Treatment start Year, then CM start Day= minimum of (Treatment Start Day or CM end Day). Otherwise CM start day = "01". Day and Month If CM start Year = Treatment start Year, then CM start Day and Month = minimum of (Treatment Start Day and Month or CM end Day and Month). Otherwise CM start Day and Month = "01 Jan". Day, Month and Year No Imputation will be performed. End Date Day If CM End Month = Study conclusion Month and CM End Year= Study conclusion Year, Then CM End Day= Study Conclusion Day. Otherwise CM End Day = last day of respective month. Day and Month If CM End Year = Study Conclusion Year, then CM End Day and Month = Study Conclusion Day and Month. Otherwise CM End Day and Month = "31 Dec".

